6. STUDY PROCEDURES

Study protocol outlined above. Additionally, we will collect Patient related outcome measures relating to breathlessness and pain each day and at day +30. We will also seek patient feedback on the protocol at this point.

7. DATA COLLECTION

Data will be collected by the trials team longitudinally. Patients surveys will be collected and the 30 day survey will be conducted via telephone consultant or face to face by the trial team

8. DATA MANAGEMENT AND CONFIDENTIALITY

Investigators are required to maintain on file the accurate, complete, and current records relating to this Study. Data will be stored securely in a locked office in a trial file. Digital information will be stored on an NHS computer in a locked office. Only authorized personnel and their designees will have access to these confidential files.

PROTOCOL DEVIATIONS

Protocol deviations should be reported to the sponsor and Chief Investigator using the provided reporting form. The Sponsor and Chief Investigator should then review the details

Feasibility of ambulatory pleurodesis
Protocol V2
IRAS: 330188
CI: [name]
26/06/2023

to assess the impact on the research dataset and also to assess if there are learning points to help prevent a repeat deviation.

MISSING DATA AND DATA QUERIES

Missing data will be included in the analysis. The trials team, CI or an appropriate designee will address any emergent data queries.

9. SAFETY REPORTING

Definitions

Adverse Event (AE) Any untoward medical occurrence in a participant, including occurrences which are not necessarily caused by or related to the intervention under study.

Adverse Reaction (AR) An untoward or unintended response in a participant to which is related to the intervention under study i.e. that a causal relationship between the trial intervention and an AE is at least a reasonable possibility and the relationship cannot be ruled out.

All cases judged by either the reporting medically qualified professional or the Sponsor as having a reasonable suspected causal relationship to the trial intervention qualify as adverse reaction.

Serious adverse Event (SAE) is any untoward medical occurrence that; results in death, is life threatening or requires inpatient hospitalisation.

Serious adverse reaction (SAR) is an event that is both serious and in the opinion of the investigator, believed with reasonable probability to be due to the trial intervention.

Unexpected Serious Adverse Reaction (USAR) is a serious adverse reaction, the nature and severity of which is not consistent with the known information about the intervention under study.

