2. BACKGROUND

AIMS AND OUTCOMES:

Patients with malignant pleural disease often experience a significant symptom burden and a short life expectancy. The cornerstone of their treatment is relieving breathlessness by draining fluid from around the lungs and attempting to prevent further fluid build up. Inpatient chest drainage and talc pleurodesis remains the most successful method of stopping the fluid build up but this often requires an average hospital stay of four days. This can be an inappropriate length of time for this patient group. Our study would investigate whether this treatment could be provided on an ambulatory basis and facilitate a greater quality of life.

We would assess deliverability of the trial protocol and collect patient feedback to see if our patients consider it an acceptable and worthwhile intervention.

3. Primary Objective

Can patients with malignant pleural effusions undergo chest drainage and talc. Pleurodesis on an ambulatory basis

Secondary Objective

What are the patient perspectives of this protocol?

Primary Outcome Measure:

Success delivery of study protocol

Secondary Outcome Measure:

Patient questionnaire

4. OVERVIEW OF STUDY PATHWAY:

Eligible patients will be offered enrolment in the trial along with standard of care options.

If patients agree to participate in the trial they would be consented for chest drain, talc pleurodesis on an ambulatory pathway.

On day 1:

- A standard chest drain would be inserted in the morning and large volume fluid removal would commence using an underwater seal bottle- as per standard care. We would remove 1000mls of fluid (stopping earlier if not tolerated) and then clamp the drain for one hour.
- We would then open the drain again and drain up to 500mls before again clamping for one hour.
- We would repeat this process as frequently as possible until the end of the working day.
- The drain would then be connected to an ambulatory bag and left in the open position.
- The patient would then be sent home to return on day 2.

On day 2:

- The drain would be flushed, aspirated and the output assessed.
- If there is still fluid output we would drain up to 500mls and close the drain for an hour and repeat.
- If there is no further output we would arrange a chest x ray to ensure the effusion has resolved and the lung has fully inflated.
- If it has we would proceed to talc slurry instillation (with 20mls 1% lidocaine as per standard practice) and clamp the drain for 2 hours.

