9.3. Recording and Reporting USARs

All USARs occurring from the intervention until 6 months post termination of trial treatment must be reported to the NHS REC. The Sponsor will perform this reporting. The assessment of expectedness will be performed by the PI against the known information for the trial. USARs must be reported no later than 15 calendar days after the Sponsor has first knowledge of the event. Any relevant follow-up information should be sought and reported as soon as possible after the initial report. As soon as a site suspects that a SAR may be a USAR they must contact the CI, sponsor representative and the trial manager immediately. The reporting timeframe starts at day 0 when the Sponsor is in receipt of a minimum set of information:

- Sponsor trial reference and trial name
- Patient trial number and date of birth
- Date of notification of the event
- Medical description of the event
- Date and time of the onset of the event (including event end date if applicable)
- Causality assessment
- Seriousness of the event, particularly if life threatening or fatal
- An identifiable reporter (e.g., Principal Investigator)

This information must be provided on USAR report form. The site is expected to fully cooperate with the Sponsor in order that a full and detailed report can be submitted to the NHS REC within the required timelines.

PIs will be informed of all USARs by the Sponsor and CI.

Feasibility of ambulatory pleurodesis
Protocol V2
IRAS: 330188
CI: [name]
26/06/2023

Responsibilities

Principal Investigator

- Checking for AEs and ARs when participants attend for treatment or follow up
- Using medical judgement in assigning seriousness and causality and providing an opinion on expectedness of events.
- Ensuring that all SAEs and SARs, including USARs, are recorded and reported to the Sponsor within 24 hours of becoming aware of the event and provide further follow-up information as soon as available.
- Ensuring that AEs and ARs are recorded and reported to the Sponsor in line with the requirements of the protocol.

Chief Investigator

- Clinical oversight of the safety of trial participants, including an ongoing review of the risk/benefit.
- Using medical judgement in assigning seriousness, causality and expectedness of SAEs where it has not been possible to obtain local medical assessment.
- Using medical judgement in assigning expectedness to SARs.
- Immediate review of all USARs.

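### The SAE definition has three criteria only, so lasting or medically important harm managed without admission is not serious on that ground alone and misses the 24-hour and USAR routes

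*Protocol*

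**What the plan says.** The definitions in Section 9 form a chain.

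- **SAE:** an untoward medical occurrence that "results in death, is life threatening or requires inpatient hospitalisation". No residual clause follows.
- **SAR:** "Serious adverse reaction (SAR) is an event that is both serious and in the opinion of the investigator". The second condition is that the investigator attributes the event to the treatment under study.
- **USAR:** "Unexpected Serious Adverse Reaction (USAR) is a serious adverse reaction" whose nature and severity do not fit what is known about the intervention.

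The reporting duties attach to that chain. The Principal Investigator's list in Section 9.3 includes "Ensuring that all SAEs and SARs, including USARs, are recorded and reported to the Sponsor within 24 hours of becoming aware of the event". Section 9.3 also states that "USARs must be reported no later than 15 calendar days after the Sponsor has first knowledge of the event"; that report goes to the NHS REC. Section 9.2 sets out a data set for each SAE, with an entry for seriousness criteria, but names no criteria of its own. For everything else the duty is "Ensuring that AEs and ARs are recorded and reported to the Sponsor in line with the requirements of the protocol", and the protocol states no time limit for such events.

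The setting is ambulatory. In Section 4, after the first day's drainage, "The patient would then be sent home to return on day 2", with the drain connected to a bag and left open.

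**The concern.** Whether an event is serious decides whether the Sponsor hears of it within a day and whether it can ever reach the ethics committee. Two of the three criteria, death and threat to life, cover only the extreme end. All other harm has to qualify through a need for admission.

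That is a poor filter in a study whose purpose is to treat people without admitting them. Participants come back on successive days, and Section 4 provides for an x-ray after drain removal to look for complications. A complication may be found and treated at such a visit. If it leaves lasting harm, or is important in the investigator's view, but neither threatens life nor needs a bed, the text classes it as non-serious.

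At stake is the speed and structure with which the Sponsor and the REC learn about the harms of the ambulatory pathway. The event itself would still be recorded.

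**Working it through.** No calculation applies. The check is to look for any other seriousness criterion in the protocol, and then to follow events through the definitions.

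**Step 1. Is the list widened elsewhere?** Sections 9 to 9.6 and the monitoring text in Section 10 contain no mention of prolonged stay, disability or medical importance as a ground for seriousness. Section 9.2 asks which seriousness criteria apply but lists none, so the form can draw only on the three in Section 9. Section 9.3 gives the Principal Investigator the task of "Using medical judgement in assigning seriousness and causality and providing an opinion on expectedness of events". This says who decides; it adds no criterion.

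**Step 2. Test events against the three criteria.** In cases A to C, assume the event neither kills nor threatens life.

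| Case | Criteria met (of 3) | SAE? | 24-hour report | USAR route (15 days) |
|---|---|---|---|---|
| A. Lasting disability, managed without admission | 0 | No | No | Closed |
| B. Medically important complication, treated at an ambulatory visit | 0 | No | No | Closed |
| C. New complication that prolongs the stay of a participant already in hospital for another reason | 0 | No | No | Closed |
| D. For contrast: complication that brings the participant into hospital | 1 | Yes | Yes | Open, if related and unexpected |

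**Step 3. Follow the consequence.** An event that is not serious cannot be a SAR, and an event that is not a SAR cannot be a USAR, however unexpected it is and however clearly related. Cases A to C therefore lose:

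- the 24-hour report to the Sponsor;
- the Section 9.2 data set, which is collected for SAEs only although that section's title also names AEs;
- the USAR report to the REC;
- the Chief Investigator's reviews in Section 9.3 of USARs and of selected SAEs and SARs.

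**Step 4. What remains for cases A to C?** The event is recorded as an AE, or as an AR if related, and reported to the Sponsor without a stated deadline.

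**Step 5. How plausible are the cases?** A and B follow directly from a pathway run through day visits. C is narrower. It needs a participant who is in hospital for a reason that was not itself the reported event, for example after withdrawal to standard care (Section 11), which Section 2 describes as an inpatient stay averaging four days. USAR reporting runs to six months after trial treatment ends, so a later stay also falls inside the window.

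**The case against.** The case on the other side has several parts, and much of it stands.

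- **Overlap.** A disabling or stay-prolonging event is still an SAE if it also threatens life or requires admission. This is right. The gap concerns events that qualify on an omitted ground alone.
- **Failed ambulatory pathway.** A reader might infer that participants whose home treatment fails and who end up in a bed are the worst affected. The text does not support this. If an untoward event caused the admission, it is already an SAE, and Section 9.2 asks for any change in condition to be sent on within 24 hours and for follow-up until resolution. Only a separate new complication, or an admission for another reason, falls through.
- **Conflict with Section 9.3.** A reader might see a contradiction between a closed list and the instruction to use medical judgement on seriousness. The two can be read together: judgement is needed to decide whether an event threatened life or required admission. The instruction does not repair the list, but it does not conflict with it.
- **Other safeguards.** AEs and ARs still go to the Sponsor. The Principal Investigator's duty on causality and expectedness is not limited to SAEs, the Chief Investigator keeps risk and benefit under review, monitors verify all adverse events, and urgent safety measures have their own immediate notification. These limit the loss to the deadline, the structured record, the serious-event reviews and the USAR route. They do not restore any of those.
- **External yardstick.** The protocol nowhere promises the omitted criteria, so conventional wording alone is no ground for criticism. The point rests instead on the protocol's own design: admission is the only route to seriousness short of threat to life, in a pathway meant to avoid admission.

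**Conclusion.** The point holds in a limited form. As written, the definition keeps lasting disability and medically important harm managed without admission out of the serious-event chain on that ground alone, together with a new complication that prolongs a stay begun for another reason. This is a stated rule that is too narrow. It is not a detail left to a statistical analysis plan, because it governs what investigators report while the study runs.

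The size cannot be put in numbers. The protocol gives no complication rate, so how often an event would be misclassified is unknown. It might be tempting to express the effect as a change in the count of serious events among the 10 patients. The protocol does not support that either: its outcomes are delivery of the protocol and a patient questionnaire, its stated analysis is thematic, and no serious-event count is planned. For the same reason it cannot be said that reported serious harm will be too low, only that an event of this kind would not be classed as serious.

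The conclusion assumes that the three criteria are applied as written and that no separate reporting form or Sponsor procedure widens them. It is a modest point, worth acting on because the change is so small.

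**What to change.** In Section 9, extend the SAE definition so that, besides the three existing criteria, an event is serious if it:

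- prolongs an existing hospitalisation;
- results in persistent or significant disability or incapacity; or
- is otherwise judged medically significant by the investigator.

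Make the seriousness entry in Section 9.2, and the SAE form, list the same criteria. SAR and USAR then take up the wider definition without separate rewording on this point.

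The cost is one sentence, matching tick boxes and a few more 24-hour reports among 10 patients. No dose, schedule, eligibility rule or sample size changes.

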9.2. Recording and Reporting AEs and SAEs

For each SAE the following information will be collected:

Feasibility of ambulatory pleurodesis
Protocol V2
IRAS: 330188
CI: [name]
26/06/2023

- Full details in medical terms and case description
 - Event duration (start and end dates, if applicable)
 - Action taken
 - Outcome
 - Seriousness criteria
 - Causality in the opinion of the investigator
 - Whether the event is considered expected or unexpected.

Any change of condition or other follow-up information should be faxed to the [Sponsor/GCTU] as soon as it is available or at least within 24 hours of the information becoming available. Events will be followed up until the event has resolved or a final outcome has been reached.

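### A serious adverse reaction has a stricter causality test and fewer judges than an adverse reaction, so some serious, unexpected, possibly related events fall outside the expedited REC report

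*Protocol*

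**What the plan says.** The definitions are in Protocol section 9, Safety Reporting.

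- **Adverse reaction (AR).** The test is that "a causal relationship between the trial intervention and an AE is at least a reasonable possibility and the relationship cannot be ruled out". The next paragraph says who may judge: an event qualifies if it is "judged by either the reporting medically qualified professional or the Sponsor as having a reasonable suspected causal relationship" to the intervention.
- **Serious adverse reaction (SAR).** This is an event that is serious and "in the opinion of the investigator, believed with reasonable probability to be due to the trial intervention".
- **USAR.** The definition begins "Unexpected Serious Adverse Reaction (USAR) is a serious adverse reaction" and adds that its nature and severity do not fit what is already known about the intervention.

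Section 9.3 attaches the external duty to the last category only: "All USARs occurring from the intervention until 6 months post termination of trial treatment must be reported to the NHS REC". The Sponsor makes that report, no later than 15 calendar days after it first knows of the event.

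Section 9.2 lists what is collected for each serious adverse event (SAE). The list includes "Causality in the opinion of the investigator" and whether the event was expected. The Responsibilities list after section 9.3 requires the Principal Investigator to pass every SAE to the Sponsor within 24 hours, whatever its cause.

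**The concern.** A reader would expect the SAR definition to be the AR definition plus seriousness. As written it differs in two ways. The threshold rises from possibility to probability, and the judges narrow from the clinician or the Sponsor to the investigator. The stricter test thus applies to the graver event, and the protocol gives no reason for it.

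What is at stake is a reporting duty. USAR status depends on SAR status, so an event that fails the SAR wording cannot reach the REC by the section 9.3 route, however unexpected it is. Section 2 describes patients with a heavy symptom burden and a short life expectancy, and the pathway sends them home with a drain in place. In that setting disease and procedure can both be plausible causes of a serious event, so a rating of possibly related is foreseeable.

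**Working it through.** No calculation applies: the protocol states no figure on this point. The check compares the definitions and follows cases through them.

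**Definitions side by side (section 9)**

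| | AR | SAR |
|---|---|---|
| Causality threshold | at least a reasonable possibility, not ruled out | reasonable probability |
| Whose judgement counts | reporting medical professional or Sponsor | investigator |
| Seriousness needed | no | yes |

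**Chain to the REC.** AR status has no REC consequence of its own. The REC report requires USAR status, which requires SAR status and unexpectedness.

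**Cases.** Every row is a serious event, so every row reaches the Sponsor as an SAE within 24 hours.

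| Causality view | Expected? | AR | SAR as written | REC report as written | SAR if defined as a serious AR | REC report then |
|---|---|---|---|---|---|---|
| Investigator: probable | no | yes | yes | yes | yes | yes |
| Investigator: possible, not probable | no | yes | **no** | **no** | yes | yes |
| Sponsor suspects, investigator does not | no | yes | **no** | **no** | yes | yes |
| Either of the two rows above | yes | yes | **no** | no | yes | no |
| Nobody suspects a link | either | no | no | no | no | no |

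The second and third rows are the gap in REC reporting. In the fourth row only the classification is wrong; the REC report is not due under either definition.

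**Does another part of section 9 close the gap?**

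- Section 9.2 records the investigator's causality opinion, the same opinion on which the SAR definition relies. It gives a differing Sponsor view no place.
- Section 9.3 tells sites to raise the alarm when they suspect that a SAR may be a USAR, so this alert also presupposes SAR status.
- Under Responsibilities, the Chief Investigator assigns causality to SAEs only when no local assessment could be had. That is a fallback, with no stated power to upgrade an investigator's rating.
- The Sponsor's listed duties are expectedness of USARs, expedited reporting to the REC and notification of sites. Causality is not among them, although the AR paragraph gives the Sponsor a say in it.

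None of these restores the second or third row to the REC route.

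**The case against.** Four objections deserve an answer.

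**Nothing is hidden from the Sponsor.** Every SAE arrives within 24 hours, with causality and expectedness recorded, and the Chief Investigator keeps risk and benefit under review and looks at specific SAEs and SARs. This stands, and it limits the consequence. It does not create a duty to report to the REC, because the SAR definition gives a Sponsor suspicion no effect.

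**Only unexpected events are affected.** This also stands. A reader might infer that every serious, possibly related event, such as worsening breathlessness, infection, admission or death, is removed from expedited reporting. The documents do not support that: any of these judged expected would not go to the REC under either wording.

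**No result of the trial is distorted.** A reader might infer that the SAR count is a main harm result, biased downwards, and that one reclassified event among 10 patients shifts a SAR rate by 1/10, or 10 percentage points. The protocol defines no such rate. Its primary outcome is delivery of the protocol, its secondary outcome is a patient questionnaire, and the analysis it states is thematic. SAEs are recorded whatever their cause, so serious-harm data are not lost.

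**The wording may simply be loose.** One can read a serious adverse reaction as an AR that is serious, treat probability as a slip for possibility, and note that the protocol sets no graded causality scale. That may be what was intended. But the SAR has its own definition, staff must work from it, and the charitable reading of the threshold still leaves the Sponsor out as a judge.

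**Conclusion.** The inconsistency is real and should be corrected. Section 9 sets two causality tests, and the nesting of USAR within SAR turns the difference into a gap in required REC reporting. The gap covers events that meet three conditions together: serious, unexpected, and either rated possibly but not probably related by the investigator or suspected as related only by the Sponsor. Serious events that meet the causality condition but are expected are affected in classification only.

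The size cannot be put as a number, because the protocol gives no expected rate of serious events, related or otherwise. With a target of 10 patients such events may be few or none.

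The conclusion assumes that the definitions are applied as written and that staff distinguish possible from probable. Without the second assumption, the mismatch over who may judge remains. What is at risk is the REC report and the SAR label, not the Sponsor's awareness of the event or any stated outcome.

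**What to change.** Replace the SAR sentence in section 9 with one that defines a SAR as any adverse reaction, as already defined in that section, that meets a seriousness criterion. The threshold and the judges are then those of the AR definition. The USAR definition and section 9.3 can stay as they are.

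Two matching edits make the change work in practice: provide a place on the SAE report for a Sponsor causality view beside the investigator's, and add that assessment to the Sponsor's listed responsibilities.

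The cost is one sentence in a protocol amendment plus the matching form text. The downside is that a few more events may need SAR review and an expectedness assessment. Data collection from patients and the analysis are unaffected.
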